The endpoints "Time to first confirmed relapse" and "PCBV from baseline to Week 108" do not add substantial information on clinically important effects of the study drug on MS disease for the following reasons:

5 December 2018, page 23/376

- The endpoint "Time to first confirmed relapse" is highly correlated to the primary endpoint of ARR. Thus, although this endpoint may provide some additional insight into the drug's effect on relapse activity, it is not expected to add relevant information to what is already available through the primary endpoint of ARR.
- The clinical significance of brain volume loss in MS and the relevance of the endpoint "PCBV from baseline to Week 108" remains unclear as the degree of change in whole brain volume measurement that results in a clinically meaningful benefit is not well defined due to several methodological limitations in brain volume measurements.
- ii. Modify the multiple testing strategy for the control of the type I error by testing the secondary endpoints according to a fallback type method. As compared to the previously planned fixed-sequence hierarchical method, this will provide some opportunity to test an endpoint later in the sequence even if an endpoint tested earlier in the sequence has failed to show statistical significance. If statistical superiority of an endpoint tested earlier in the sequence can be shown the corresponding alpha can be passed on to endpoints later in the sequence. As a consequence, endpoints tested late in a fallback sequence are given a higher weight as compared to endpoints at the beginning of the sequence. This is in contrast to the previous planned hierarchical fixed sequence approach where endpoints at the beginning of the sequence receive a higher weight. To maintain the same weight ranking of the secondary endpoints it is proposed to change the order in the sequence.

The hypothesis for the primary endpoint of ARR is first tested with the full alpha. If the primary endpoint null hypothesis is rejected, the alpha will be split evenly (1/3 of alpha) between the following three secondary endpoints using the fallback procedure, allowing for passing on alpha as per the following sequence:

- Change from baseline to Week 108 in fatigue-related symptoms as measured by the symptoms domain of the FSIQ–RMS [Fatigue]
- Cumulative number of CUAL from baseline to Week 108 [CUALs]
- Time to 12-week CDA from baseline to EOS [12-week CDA]

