12-lead ECG*	* (9)	Х	Х	Х	Х	Х	Х		Х	X(9)	Х	
Pulse rate*								Х	X(20)			
Ophthalmological examination / OCT*					×				х			
Pulmonary fur	nction tests** (11)				Х	Х	Х		Х			
Hematology/C	Chemistry**(fasted)	Х	Х	Х	Х	Х	Х		Х			
Urinalysis	•		Х		Х	Х			Х			
Viral serology	,	1							Х			
Pregnancy tes	t*/** (12)	Х	Х	Х	Х	Х	X (12)		Х			
Serum sample	vaccination* (13)								Х			

Ponesimod / ACT-128800 Relapsing multiple sclerosis Protocol AC-058B301, OPTIMUM Version 7

Confidential

EudraCT 2012-000540-10 Doc No D-18.388

5 December 2018, page 49/376

PK sampling for ponesimod*				Х				X (14)		
Teriflunomide plasma concentration								X (23)		
Accelerated elimination procedure				Х	X (15)					
Accelerated elimination procedure					x	X (24)				
compliance review						,				
Study drug dispensing/accountability (16)	Х	Х	Х	Х			Х	Х	Х	Х
AEs/SAEs* (17)	Х	Х	Х	Х	Х	Х	Х	Х	Х	х

*Data collected in the eCRF

**Electronically transferred to sponsor.

Day 1 (date of randomization visit) is to be used as the reference date for the purpose of calculating the subsequent visit dates (and time windows).

- (1) At every study visit, subjects are reminded to contact their principal investigator / treating neurologist at the clinical site immediately in the event of the appearance of any new or worsening neurological symptoms. In addition, the site will contact the subject in between the 12-weekly visits (e.g., Visit 6–Week 12, Visit 7–Week 24,...) in order to proactively inquire about any new or worsened neurological symptoms. These telephone calls will be conducted either at Weeks 18, 30, 42, 54, 66, 78, 90, and 102 (+/- 7 days), or 6 weeks after the last 12-weekly visit (+/- 7 days). Whenever, between visits, a subject experiences any new or worsening neurological symptoms, he/she must contact the principal investigator / treating neurologist, study nurse or clinical coordinator as soon as possible in order to complete a relapse assessment questionnaire [see Appendix 17].
- (2) The symptoms scale (with a 24-h recall) will be completed for 7 consecutive days (the day of the visit and the 6 days after the visit).
- (3) Health care resource utilization data, number of intensive care unit admission for MS relapses and emergency medical services facility visits for MS.
- (4) Only for subjects-participating in the patient preference sub-study. The Multiple Sclerosis Patient Preference Questionnaire will be completed at home during follow-up period (before Visit 15 [FU1]).

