- (16) Scheduled study medication dispensing/return procedures may be adapted according to the site practice.
- (17) All AEs and SAEs that occur after signing the Informed Consent Form and up to 30 days after study treatment discontinuation must be reported.
- (18) The EOT visit will take place at Week 108 (or earlier in case of premature discontinuation of study drug). In all cases, the EOT visit should take place 1 day after the last dose of study drug but no later than 7 days after the last dose of study drug.
- (19) Unscheduled visits may be performed at any time during the study and may include all or some of the indicated assessments, based on the judgment of the investigator.
- (20) Only if no 12-lead ECG is performed at this visit.
- (21) Only at unscheduled visits when the subject meets with the treating neurologist (but not at other unscheduled visits (e.g., conducted for repeat ALT or AST testing, repeat PFT testing,...).
- (22) For subjects not continuing in the AC-058B303 extension study, FU2 will be performed 30 to 37 days after last study drug intake. For subjects continuing in the AC-058B303 extension study, an abbreviated FU2 will be performed 23 to 37days after last study drug intake, if needed for compliance reasons. The abbreviated FU2 should include: Accelerated elimination procedure compliance review, AEs/SAEs, relapse, concomitant medications
- (23) The testing of teriflunomide plasma concentration may be conducted for women of childbearing potential and fertile male subjects, if needed to confirm that contraception may be discontinued. Teriflunomide plasma concentration can also be assessed for any subjects not entering the extension study if deemed necessary for the subject's safety, at the investigator's discretion. Testing must not be conducted earlier than i) 20 weeks after last drug intake if the subject's compliance with the accelerated elimination procedure has been assessed as sufficient [see Section 5.1.14.2]; ii) 35 weeks (i.e., 8 months) after last drug intake or EOS, whichever is last, if the subject's compliance with the accelerated elimination procedure has not been assessed as sufficient.
- (24) Only if the accelerated elimination procedure has been repeated or missing intake was completed after FU1.

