1.3.2.2 Pharmacodynamics in humans

Oral administration of ponesimod dose-dependently reduces the circulating lymphocyte count in humans. The maximum reduction from baseline of approximately 65–80% is achieved after a single dose of \geq 50 mg, or 40 mg o.d. at steady state. The nadir in lymphocyte count is attained within 6–10 h following a given single dose. There is no evidence of tachyphylaxis on lymphocyte count. Peripheral blood counts of both T and B cells are reduced by ponesimod, while NK cells and neutrophils are not reduced. Food, race and gender do not appear to relevantly affect the PD of ponesimod. Upon discontinuation of ponesimod, the lymphocyte count generally returns to within the normal range within 1 week.

The magnitude of lymphocyte-count reductions seen with ponesimod in MS subjects was consistent with observations made after short-term treatment in healthy subjects. In the Phase 2 dose-finding study AC-058B201, at Week 24, the mean reductions from baseline in lymphocyte count were 49.8%, 65.3% and 68.6% in the ponesimod 10 mg, 20 mg, and 40 mg groups, respectively, compared to a mean increase of 3.3% in the placebo group. Lymphocyte counts remained stable on treatment and returned to baseline levels within 1 week following ponesimod treatment discontinuation.

More detailed information can be found in the IB [Ponesimod IB].

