5.1.14 Elimination of teriflunomide

5.1.14.1 Accelerated elimination procedure for teriflunomide

Teriflunomide is eliminated slowly from plasma. Without an accelerated elimination procedure, it takes on average 8 months to reach plasma concentrations less than 0.02 mg/L, although because of individual variations in drug clearance it may take as long as 2 years.

At EOT, all subjects will have to undergo an accelerated elimination procedure consisting of either of the following procedures:

- Administration of cholestyramine 8 g three times a day (i.e., every 8 h) for 11 days. If cholestyramine 8 g three times a day is not well tolerated, cholestyramine 4 g three times a day can be used.
- Administration of 50 g oral activated charcoal two times a day (i.e., every 12 h) for 11 days.

If either elimination procedure is poorly tolerated, treatment days do not need to be consecutive unless there is a need to lower teriflunomide plasma concentration rapidly. It is permissible to switch from cholestyramine to activated charcoal (or vice versa) for reasons of tolerability.

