6.1.2 Secondary efficacy endpoints

There are four secondary efficacy endpoints, which will be analyzed as per the statistical testing strategy outlined in Section 11.3.1:

- Change from baseline to Week 108 in fatigue-related symptoms as measured by the symptoms domain of the FSIQ-RMS
- Cumulative number of combined unique active lesions (CUAL) from baseline to Week 108

Definition: CUAL are new Gd+ T1 lesions plus new or enlarging T2 lesions (without double-counting of lesions).

• Time to 12-week CDA from baseline to EOS

Definition: A 12-week CDA is an increase of at least 1.5 in EDSS for subjects with a baseline EDSS score of 0.0 or an increase of at least 1.0 in EDSS for subjects with a baseline EDSS score of 1.0 to 5.0, or an increase of at least 0.5 in EDSS for subjects with a baseline EDSS score \geq 5.5 which is to be confirmed after 12 weeks.

Baseline EDSS is defined as the last EDSS score recorded prior to randomization. The initial EDSS increase, meeting the above criteria, is defined as the onset of disability accumulation.

All EDSS measurements (with or without relapse, at a scheduled or unscheduled visit) will be used to determine the onset of disability accumulation. However, EDSS scores used for confirmation of disability accumulation must be obtained at a scheduled visit (i.e., unscheduled visits cannot be used as confirmatory visits) outside any ongoing relapse. In this context, relapse duration is defined as period between start and end dates if available Ponesimod / ACT-128800 Relapsing multiple sclerosis Protocol AC-058B301, OPTIMUM Version 7 5 December 2018, page 119/376

Confidential

and limited to 90 days from onset if end date is not available or duration is longer than 90 days.

In order to confirm that the EDSS increase is persistent, all EDSS measurements between the onset and the 12-week EDSS confirmation (minus 7-day visit time-window) need to show an increase in EDSS, meeting the criteria for accumulation of disability as defined above.

• Time to 24-week CDA from baseline to EOS

Definition: A 24-week CDA is an increase of at least 1.5 in EDSS for subjects with a baseline EDSS score of 0.0 or an increase of at least 1.0 in EDSS for subjects with a baseline EDSS score of 1.0 to 5.0, or an increase of at least 0.5 in EDSS for subjects with a baseline EDSS score \geq 5.5 which is to be confirmed after 24 weeks.

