Once the results from the laboratory assessments confirm the subject's eligibility, and provided no other assessment performed in the meantime excludes the subject, the site coordinator will contact and ask the subject to start the completion of the FSIQ-RMS. At home, the subject will complete the symptom domain of the FSIQ-RMS for 7 days (i.e., section 1 of the questionnaire). On the seventh day, the subject will also complete the impact domain of the FSIQ-RMS (i.e., section 2 of the questionnaire). The information captured from this assessment will be used as the baseline data for the FSIQ-RMS. Ideally, the FSIQ-RMS will be completed during the 7 consecutive days preceding the randomization.

After randomization, the symptoms domain of the FSIQ-RMS (i.e., section 1 of the questionnaire) will be completed by the subject at home on a daily basis, starting in the evening of the day of a visit when the FSIQ-RMS is administered (Day 1 of questionnaire administration cycle) and during the 6 subsequent days (i.e., over 7 days in total). Subjects will return the completed FSIQ-RMS diary at the next scheduled visit. On the seventh day, the subject will also complete the impact domain of the FSIQ-RMS (i.e., section 2 of the questionnaire). If applicable, at the end of the PTOP, the FSIQ-RMS will be completed prior to Visit 14A (Week 108), ideally, during the 7 consecutive days preceding the visit.

The data from the electronic device will be collected by the vendor who will send the results to Actelion. The individual questionnaires will be completed only in countries for which validated translations are available.

A sample of the FSIQ-RMS is provided as Appendix 9.

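### As written, a completer's Week 108 FSIQ-RMS fatigue diary is filled in entirely after the last dose and largely during the elimination procedure

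*Protocol*

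**What the plan says.** The endpoint is listed in Section 6.1.2 as "Change from baseline to Week 108 in fatigue-related symptoms as measured by the symptoms domain of the FSIQ-RMS". Under the Amendment 6 rationale, once the primary null hypothesis is rejected, "the alpha will be split evenly (1/3 of alpha) between the following three secondary endpoints using the fallback procedure". Fatigue comes first in that sequence.

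Four rules fix when the Week 108 diary is completed:

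- **Visit timing.** Table 2, footnote (18): "the EOT visit should take place 1 day after the last dose of study drug but no later than 7 days" after it. Section 3.1.2 gives the same window.
- **Diary timing.** Section 7.2.7 has the symptom domain (24-h recall) completed at home, "starting in the evening of the day of a visit when the FSIQ-RMS is administered (Day 1 of questionnaire administration cycle"), and on the six following days. Table 2, footnote (2), which covers EOT, says it "will be completed for 7 consecutive days (the day of the visit and the 6 days after the visit") and makes no exception for EOT.
- **Elimination procedure.** Section 5.1.14.1: "At EOT, all subjects will have to undergo an accelerated elimination procedure consisting of either of the following procedures". Both options last 11 days.
- **Diaries completed beforehand.** The baseline diary is ideally completed in the week before randomization. For subjects in the post-treatment observation period (PTOP), "the FSIQ-RMS will be completed prior to Visit 14A (Week 108), ideally, during the 7 consecutive days preceding the visit".

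**The concern.** Section 1.4 describes a comparison of ponesimod with teriflunomide over a 108-week treatment period. For fatigue, the rules above place the completer's Week 108 measurement after that period has ended, while subjects in both arms take cholestyramine or activated charcoal. Section 5.1.14.1 itself allows for the procedure being poorly tolerated. A daily fatigue score taken then reflects early withdrawal of study drug plus a non-study treatment, so a result in either direction is harder to attribute to the randomized treatments as taken.

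Two timings also enter one endpoint. Completers give a post-visit diary, whereas PTOP subjects give a pre-visit diary at Visit 14A.

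Fatigue is tested at one third of alpha, 0.05/3 = 0.0167. If it fails, its share is not passed on. 12-week CDA could then reach at most two thirds of alpha, 2 × 0.0167 = 0.0333, rather than 0.05.

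**Working it through.** The plan states no figure for this point, so there is nothing to reproduce. The check is a day count.

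**Inputs.** Last dose = Day 0, in the morning. EOT visit on Day v, with v from 1 to 7 (Table 2 footnote (18); Section 3.1.2). Diary on Days v to v+6 (Section 7.2.7; Table 2 footnote (2)). Elimination procedure for 11 days from EOT (Section 5.1.14.1), taken as Days v to v+10 or, if it starts the next day, v+1 to v+11. Ponesimod half-life about 32 h (Section 1.3.2.1).

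**Day count.**

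| EOT visit | Diary days | Diary days that are dosing days | Overlap, elimination starts on visit day | Overlap, starts next day |
|---|---|---|---|---|
| Day +1 | +1 to +7 | 0 of 7 | 7 of 7 | 6 of 7 |
| Day +2 | +2 to +8 | 0 of 7 | 7 of 7 | 6 of 7 |
| Day +7 | +7 to +13 | 0 of 7 | 7 of 7 | 6 of 7 |

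**Residual ponesimod, as context only.** Fraction of the level at the last dose on Day d = 2^(−(24d + 10)/32). The 10 h for an evening entry is an assumption.

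- Visit on Day +1: 2^(−34/32) = 0.479 on the first evening, then 0.285, 0.169, 0.101, 0.060, 0.036 and 0.021. Mean about 0.16.
- Visit on Day +7: 0.021 falling to 0.001. Mean about 0.007.
- Without the 10 h shift, the means are 0.20 and 0.009.

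These figures ignore any effect of the elimination procedure on ponesimod. The protocol gives no rate of teriflunomide decline under the procedure, so the comparator's residual cannot be computed.

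**Other visits.** At Weeks 12, 24, 60 and 84 the same post-visit rule gives an on-drug diary for subjects still on treatment. Only EOT is affected.

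**Earlier windows elsewhere at EOT.** Sections 7.3.5 (spirometry), 7.3.6 (DLco), 7.3.9 (ophthalmology) and 7.3.10 (OCT) each allow testing up to 7 days before the EOT visit. Section 7.2.7 has no such allowance.

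**Candidate remedies.**

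- Visit 14A wording applied to EOT (Days v−7 to v−1): 7 of 7 dosing days for a Day +1 visit, 6 of 7 for Day +2, and 1 of 7 for Day +7.
- Diary tied to the last dose (Days −6 to 0): 7 of 7 dosing days whatever the visit date.

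**The case against.** The strongest reply is that the full EOT text is not visible. Amendment 6 says that certain unnamed EOT assessments may be done up to 7 days before the last intake, and it lists Section 8.2.10 as amended. That section is not in the text available here and could cover the FSIQ-RMS. This stands as a limit: it cannot be said that no exception exists anywhere. But the wording is permissive, and an exception there would contradict Section 7.2.7 and Table 2 footnote (2), so the passages would still need reconciling.

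A reader might infer that the Week 108 value says nothing about fatigue on treatment, or that a true difference must be attenuated. The documents support neither. Section 1.3.2.2 reports that "Lymphocyte counts remained stable on treatment and returned to baseline levels within 1 week following ponesimod treatment discontinuation", but that concerns lymphocytes. Nothing links fatigue to current drug level, and a difference built up over 108 weeks need not vanish in days. With a Day +1 visit, the first 24-h recall also overlaps the last dosing interval. A loss-of-power figure would need an assumed design power and an assumed loss of effect, and the protocol text available gives neither.

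Nor does the Visit 14A exception show that washout was recognized as a problem. Diaries are returned at the next visit, and 14A is usually the last one, so logistics may explain it.

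The repeated-measures ANCOVA announced in Amendment 6 uses all scheduled visits. That helps a supportive Week 84 estimate but does not change when the Week 108 data are collected. Finally, failure on fatigue does not block CUAL or CDA; they lose only the alpha that would have been passed on.

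**Conclusion.** The point holds as a matter of timing. Under Section 7.2.7 and Table 2 footnote (2), 0 of 7 entries in a completer's Week 108 symptom diary fall on a dosing day. Six or seven overlap the elimination procedure, depending on whether it starts on the visit day or the day after. The endpoint also combines post-visit diaries (EOT) with pre-visit diaries (Visit 14A).

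The conclusion assumes that Section 8.2.10 does not move the diary earlier. If it does, the finding becomes a contradiction to be reconciled.

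No direction or size of bias is claimed: washout may differ between arms, and the effect of the elimination agents on reported fatigue is not given. The primary endpoint is unaffected. This should be fixed because an alpha-bearing endpoint is measured under avoidably poor conditions, but it does not put the trial's main conclusion at risk.

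**What to change.** In Section 7.2.7 and Table 2 footnote (2), state that at the planned Week 108 EOT the FSIQ-RMS is completed on the 7 consecutive days ending on the day of the last dose, before the elimination procedure starts. The impact domain stays on the seventh day. Reconcile this with Section 8.2.10. Do not simply reuse the Visit 14A wording, which would leave only 1 of 7 dosing days when the EOT visit is on Day +7.

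Before unblinding, flag every EOT diary collected after the last dose. Pre-specify a supportive treatment comparison at Week 84, the last on-treatment diary under the current schedule, and a sensitivity analysis of the Week 108 result by diary timing.

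The cost is protocol wording, a changed trigger in the electronic diary and a note to sites. No visit is added and dosing is untouched. The real downside is that completers' Week 108 diaries from before and after the change will differ in timing. This version is dated December 2018 and the first amendment April 2015, so many EOT diaries may already exist, although enrolment dates are not shown. If most completers are past EOT, the flag and the two added analyses carry most of the benefit. The Week 84 estimate needs no new data, but it describes a time point 24 weeks earlier (108 − 84).

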7.2.8 Patient preferences

Patient preferences for several treatment outcomes will be assessed in a subset of approximately 360 subjects using an electronic questionnaire developed by Actelion. Subjects will be recruited at selected sites in countries for which translations are available. Only subjects who consent under a separate informed consent for MS Patient Preference Questionnaire will participate in the sub-study. The MS Patient Preference Questionnaire will be completed at home twice during the pre-randomization period (after Visits 1 and 2 [Screening, Baseline]), and during the follow-up period (before Visit 15, FU1) using an electronic device. All questionnaire responses will be electronically transferred to the Actelion database. Support for navigating the questionnaire will be provided as a tutorial within the electronic device. No guidance as to the content of the responses will be provided to the subject.

A sample of the MS Patient Preference Questionnaire is provided as Appendix 14.

7.2.9 Patient's Global Impression of Severity of Fatigue

The PGI-S of Fatigue assesses the subject's fatigue severity on a given day. The scale is scored by the subject on an 11-point numeric rating scale ranging from 0 to 10, anchored at 0 = "Not severe at all" and 10 = "Very severe". The questionnaire will be administered in an electronic format.

PGI-S of Fatigue will be completed during the pre-randomization period at Visit 2 (Baseline), at Visits 6, 7, 10, and 12 (Weeks 12, 24, 60, 84), 14 (EOT), and at unscheduled visits due to relapses (R1, R2, etc.) or other unscheduled visits (U1, U2, etc.). If applicable, PGI-S will also be performed at the corresponding visits in the PTOP.

The individual questionnaires will be completed only in countries for which validated translations are available.

It is recommended that the PGI-S of Fatigue is completed prior to any clinical assessments and before study drug exposure on the day of the visit. Preferably, subjects would complete the PGI-S of Fatigue while waiting for their appointment before any interaction with health care providers to avoid any potential bias or impact of interventions in their responses.

A sample of the PGI-S of Fatigue is provided as Appendix 12.

